			Injection Phase														Follow-up Phase										
Injection 1	Within 7 and/or 5 days of admission to the clinic ³	Inj 1 Day -1	Inj 1 Day 1				Inj 1 Day 2	Inj 1 Day 3	Inj 1 Day 4	Inj 1 Day 5	Inj 1 Day 6	Inj 1 Day 7	Inj 1 Day 8	Inj 1 Day 10	Inj 1 Day 14	Inj 1 Day 17	Inj 1 Day 22	Inj 1 Day 28 - proceed to Inj 2 Day 1	Follow-up post last injection								
Injection 2	Within 7 and/or 5 days of admission to the clinic ³	Inj 2 Day -1	Inj 2 Day 1				Inj 2 Day 2	Inj 2 Day 3	Inj 2 Day 4	Inj 2 Day 5	Inj 2 Day 6	Inj 2 Day 7	Inj 2 Day 8	Inj 2 Day 10	Inj 2 Day 14	Inj 2 Day 17	Inj 2 Day 22	Inj 2 Day 28 - proceed to follow-up	Week 4/ Day 28	Week 8	Week 12	Week 20	Week 28	Week 36	Week 44	Week 52 / EW ¹	
Procedures			Pre-dose ²	1 h	2 h	8 h	24 h																				
CCI																											
CCI																											
Provide diary card regarding injection site reactions			X																								
Discharge from the clinic												X															
Injection site reaction assessment ¹⁰				X	X	X	X	X	X	X	X	X	X	X	X	X	X		X	X	X	X	X	X	X	X	
AE Assessment ⁶				X	X	X	X	X	X	X	X	X	X	X	X	X	X		X	X	X	X	X	X	X	X	
Concomitant Medication Review				X	X	X	X	X	X	X	X	X	X	X	X	X	X		X	X	X	X	X	X	X	X	

			Injection Phase														Follow-up Phase									
Injection 1	Within 7 and/or 5 days of admission to the clinic ³	Inj 1 Day -1	Inj 1 Day 1				Inj 1 Day 2	Inj 1 Day 3	Inj 1 Day 4	Inj 1 Day 5	Inj 1 Day 6	Inj 1 Day 7	Inj 1 Day 8	Inj 1 Day 10	Inj 1 Day 14	Inj 1 Day 17	Inj 1 Day 22	Inj 1 Day 28 – proceed to Inj 2 Day 1	Follow-up post last injection							
Injection 2	Within 7 and/or 5 days of admission to the clinic ³	Inj 2 Day -1	Inj 2 Day 1				Inj 2 Day 2	Inj 2 Day 3	Inj 2 Day 4	Inj 2 Day 5	Inj 2 Day 6	Inj 2 Day 7	Inj 2 Day 8	Inj 2 Day 10	Inj 2 Day 14	Inj 2 Day 17	Inj 2 Day 22	Inj 2 Day 28 – proceed to follow-up	Week 4/ Day 28	Week 8	Week 12	Week 20	Week 28	Week 36	Week 44	Week 52 / EW ¹
Procedures			Pre-dose ²	1 h	2 h	8 h	24 h																			
Blood plasma PK Sampling ⁷			X	X	X	X	X	X	X	X	X	X	X	X	X	X	X		X	X	X	X	X	X	X	X

- Participants will have PK monitoring up to and including Week 52 post last injection. Participants with undetectable CAB concentrations before this timepoint will be deemed to have completed follow up and return to the clinic for a last study visit at which activities specified for the Week 52/EW visit will be performed. Participants who withdraw from the study before week 52 post last injection will be asked to return to the site for a withdrawal visit.

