Due to slower than anticipated enrolment, the sponsor has decided to conduct an additional unblinded preliminary interim analysis of Cohort 1-5 data for the purpose of timely study results dissemination, which will take place before all participants in cohort 4b have completed injection phase assessments (i.e., injection 2 Week 4). Participants in all other cohorts will have completed the primary injection phase assessments, and all follow-up phase assessments for cohorts 1-3.

Data displays for the preliminary Cohort 1-5 interim analysis will exclude Cohort 4b data from participants who have received injection 1 but have not yet completed Injection 2 Day 1 or Follow-up Week 4 by the data analysis cut-off. Cohort 4b will remain blinded to the randomized mitigation treatments **CCI** and results will not be presented by mitigation group for the interim analysis. All other cohorts will be unblinded.

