4. ANALYSIS POPULATIONS

For the Cohort 1-5 preliminary interim analysis, displays will exclude Cohort 4b data from participants who have received injection 1 but have not yet completed Injection 2 Day 1 or Follow-up Week 4 by the data analysis cut-off. Cohort 4b will remain blinded to the randomized mitigation treatments **CCI** and results will not be presented by mitigation group for the interim analysis.

Population	Definition / Criteria	Analyses Evaluated
Screened	All participants who were screened for eligibility.	
 Study Population
Enrolled	
All participants who passed screening and entered the study.
 
Note: screening failures (who never passed screening even if rescreened) and participants screened but never enrolled into the study are excluded from the Enrolled population as they did not enter the study.
	
 Study Population
Randomized	All participants who were randomly assigned to treatment in the study.	
 Study Population
Safety	
All participants who received at least one dose of study treatment (oral or injection).
 
This population will be based on the treatment the participant received.
	
 Safety, Baseline and Demographic Characteristics
Safety – LA Exposed	
All participants who received at least one injection of long-acting study treatment.
 
This population will be based on the treatment the participant received.
	
 Injection Site Reactions
Pharmacokinetic	
All participants in the Safety population who received study treatment and had at least 1 non-missing PK assessment (non-quantifiable [NQ] values will be considered as non-missing values).
 
Note: PK samples that may be affected by protocol deviations will be reviewed by the study team to determine whether or not the sample will be excluded.
	
 PK Concentration and PK Parameter

Refer to [Appendix 10: List of Data Displays](#) which details the population used for each display.

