10.10.9. ICH Listings

ICH: Listings					
No.	Population	GSK Standard / Example Shell	Title	Programming Notes	Deliverable [Priority]
Subject Disposition					
1.	Randomized	TA1	Listing of Randomized and Actual Treatments – Part 1 & Part 2		Cohort 1-5, EOS
2.	Screened	ES7	Listing of Reasons for Screen Failure		Cohort 1-5, EOS
3.	Safety	ES2	Listing of Reasons for Study Withdrawal – Part 1 & Part 2		Cohort 1-5 IA Cohort 1-4, Cohort 1-5, EOS
4.	Safety	SD2xo	Listing of Reasons for Study Treatment Discontinuation – Part 1 & Part 2		Cohort 1-5 IA Cohort 1-4, Cohort 1-5, EOS
5.	Safety	BL1	Listing of Subjects for Whom the Treatment Blind was Broken During the Study – Part 1 & Part 2		Cohort 1-5, EOS
Protocol Deviations					
6.	Safety	DV2xo	Listing of Protocol Deviations (Important and/or COVID-19 Related) – Part 1 & Part 2		Cohort 1-5, EOS
7.	Safety	IE3	Listing of Subjects with Inclusion/Exclusion Criteria Deviations – Part 1 & Part 2		Cohort 1-5, EOS
Populations Analysed					
8.	Safety	SP3xo	Listing of Subjects Excluded from Any Population – Part 1 & Part 2		Cohort 1-5, EOS
Demographic and Baseline Characteristics					
9.	Safety	DM2	Listing of Demographic Characteristics – Part 1 & Part 2		Cohort 1-5, EOS
10.	Safety	DM9	Listing of Race – Part 1 & Part 2		Cohort 1-5, EOS
Concomitant Medication and Medical History					

ICH: Listings					
No.	Population	GSK Standard / Example Shell	Title	Programming Notes	Deliverable [Priority]
11.	Safety	CM3xo	Listing of Concomitant Medications – Part 1 & Part 2	Based on GSK Drug Dictionary	Cohort 1-5, EOS
12.	Safety	MH2	Listing of General Medical History – Part 1 & Part 2		Cohort 1-5, EOS
Exposure and Treatment Compliance					
13.	Safety	EX3	Listing of Exposure Data – Part 1	CCI	Cohort 1-5, EOS
14.	Safety	POP_L1	Listing of Drug Accountability for Oral CAB – Part 1 & Part 2		Cohort 1-5, EOS
Adverse Events					
15.	Safety	AE2	Listing of Relationship Between System Organ Class and Verbatim Text		Cohort 1-5, EOS
16.	Safety	AE7	Listing of Subject Numbers for Individual Adverse Events – Part 1 & Part 2		Cohort 1-5, EOS
17.	Safety	AE8CPxo	Listing of All Adverse Events – Part 1 & Part 2		Cohort 1-5 IA Cohort 1-4, Cohort 1-5, EOS
18.	Safety	AE8CPxo	Listing of Injection Site Reaction Adverse Events – Part 1 & Part 2	Include variable from the AE ISR form: “Did the subject use or apply any treatment at home for the injection site related symptom?”	Cohort 1-5, EOS

ICH: Listings					

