No.	Population	GSK Standard / Example Shell	Title	Programming Notes	Deliverable [Priority]
19.	Safety	SAFE_L1	Listing of Details of Injection Site Reaction Adverse Events – Part 1 & Part 2	Include additional variables collected on the impact on social & functional activities forms	Cohort 1-5, EOS
20.	Safety	AE8CPxo	Listing of Serious Adverse Events (Fatal & Non-Fatal) – Part 1 & Part 2		Cohort 1-5 IA Cohort 1-4, Cohort 1-5, EOS
21.	Safety	AE14	Listing of Reasons for Considering as a Serious Adverse Event – Part 1 & Part 2		Cohort 1-5, EOS
22.	Safety	AE8CPxo	Listing of Adverse Events Leading to Treatment Discontinuation and/or Withdrawal from Study – Part 1 & Part 2		Cohort 1-5 IA Cohort 1-4, Cohort 1-5, EOS
COVID-19 Assessment					
23.	Safety	AE8CPxo	Listing of COVID-19 Related Adverse Events – Part 1 & Part 2		Cohort 1-5, EOS
24.	Safety	PAN12	Listing of COVID-19 Assessments and Symptom Assessments for Subject with COVID-19 Adverse Events – Part 1 & Part 2		Cohort 1-5, EOS
25.	Safety	PAN7	Listing of All Subjects with Visits and Assessments Impacted by COVID-19 Pandemic – Part 1 & Part 2		Cohort 1-5, EOS
All Laboratory					
26.	Safety	LB5xo	Listing of All Clinical Chemistry Data for Subjects with any Toxicities – Part 1 & Part 2		Cohort 1-5, EOS
27.	Safety	LB5xo	Listing of All Hematology Data for Subjects with any Toxicities – Part 1 & Part 2		Cohort 1-5, EOS
28.	Safety	LB5xo	Listing of All Coagulation Data for Subjects with any Toxicities – Part 1 & Part 2		Cohort 1-5, EOS

CONFIDENTIAL

212482

ICH: Listings					
No.	Population	GSK Standard / Example Shell	Title	Programming Notes	Deliverable [Priority]
ECG					
29.	Safety	EG5xo	Listing of All ECG Findings for Subjects with an Abnormal Finding – Part 1 & Part 2		Cohort 1-5, EOS
30.	Safety	EG3xo	Listing of All ECG Values for Subjects with Any Value of Potential Clinical Importance – Part 1 & Part 2		Cohort 1-5, EOS
Vital Sign					
31.	Safety	VS4xo	Listing of All Vital Signs for Subjects with Values of Potential Clinical Importance – Part 1 & Part 2		Cohort 1-5, EOS
Liver Event					
32.	Safety	LIVER5	Listing of Liver Monitoring/Stopping Event Reporting – Part 1 & Part 2		Cohort 1-5, EOS
33.	Enrolled	LIVER15	Liver Stopping Event Profile		Cohort 1-5, EOS
Questionnaire					
34.	Safety	SAFE_L3	Listing of Numeric Rating Scale – Part 1 & Part 2		Cohort 1-5, EOS
35.	Safety	SAFE_L4	Listing of Perception of Injection – Part 1 & Part 2		Cohort 1-5, EOS
Immunogenicity					

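### Read literally, the Cohort 1-5 interim exclusion can drop a Cohort 4b participant who left the study between Injection 1 and Week 4, and with them their withdrawal and safety data

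*SAP*

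**What the plan says.** SAP 3.2 adds an unblinded preliminary interim analysis of Cohorts 1-5 so that results can be disseminated sooner, "which will take place before all participants in cohort 4b have completed injection phase assessments". At the cut-off, its outputs must "exclude Cohort 4b data from participants who have received injection 1 but have not yet completed Injection 2 Day 1 or Follow-up Week 4". SAP 4 repeats the rule ("For the Cohort 1-5 preliminary interim analysis, displays will exclude Cohort 4b data from participants who have received injection 1", with the same visit condition), and SAP 10.10.3 attaches it to the Cohort 1-5 IA deliverable. None of the three places mentions participants who have left the study.

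SAP 10.10 marks these displays, among others, for that deliverable:

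- Listing 3 (study withdrawal), Listing 4 ("Listing of Reasons for Study Treatment Discontinuation"), Listing 17 (all AEs), Listing 20 (SAEs) and Listing 22 ("Listing of Adverse Events Leading to Treatment Discontinuation and/or Withdrawal from Study");
- Tables 2.2-2.4 (injection-site reactions) and Tables 2.9-2.10 (AEs by maximum grade).

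The population that SAP 4 defines for injection-site reactions is "All participants who received at least one injection of long-acting study treatment".

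On participants who stop:

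- SAP 10.7.1 keeps the data of withdrawn participants in listings, tables and figures, but only where the SAP does not specify something else.
- Protocol 7.1 keeps a participant who stops injections in follow-up unless consent is withdrawn.
- Protocol 7.2 allows withdrawal from the study itself at any time.
- Protocol 1.3.3, footnote 1, adds: "Participants who withdraw from the study before week 52 post last injection will be asked to return to the site for a withdrawal visit". In the schedule that visit shares the Week 52 column, not the Week 4 column.

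**The concern.** The rule appears meant to hold back people who are part-way between injections at the cut-off. It uses visit completion as a stand-in for being in progress, and the stand-in fails for someone who has left: that person has not completed the visit and never will.

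Exclusion could then depend on the outcome being displayed. A participant who leaves because of a reaction to Injection 1 would be missing from the reaction tables, and an SAE followed by an early exit would be missing from the SAE listing. Cohort 4b gives subcutaneous injections with topical NSAID or steroid treatment, so local tolerability is central to it. With 24 participants, one or two people change the picture.

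**Working it through.** The plan states no figure on this point, so there is nothing to reproduce. The check has two parts.

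**1. Who is excluded.** I applied the rule to each possible state at the cut-off under three readings: (A) neither visit completed, the natural reading; (B) either visit missing; (C) only participants still in the study with neither visit completed.

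| State at cut-off | A | B | C |
|---|---|---|---|
| Withdrew during oral lead-in | keep | keep | keep |
| Injection 1, in study, before Week 4 | exclude | exclude | exclude |
| **Injection 1, left study before Week 4** | **exclude** | **exclude** | **keep** |
| Injection 1 only, attended Follow-up Week 4 | keep | exclude | keep |
| Injection 2 Day 1 done, in study | keep | exclude | keep |
| Injection 2 Day 1 done, left before Follow-up Week 4 | keep | exclude | keep |
| Both visits completed | keep | keep | keep |

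The early leaver is lost under A and B. Only C, which adds a condition that the SAP does not state, keeps that person.

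**2. Possible size (illustration).** Inputs: 24 participants in Cohort 4b (Protocol 4.1.1). The number of leavers, k, is assumed. Assume also that all 24 are injected and that the other 24 − k have reached Injection 2 Day 1. This is compatible with the interim's timing, because some may still be short of Injection 2 Week 4.

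Withdrawals between Injection 1 and Week 4 are displayed as 0/(24 − k); the full figure is k/24. For a reaction that 4 stayers and every leaver had (the extreme case), the displayed rate is 4/(24 − k) and the full rate is (4 + k)/24.

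| k | Withdrawals shown | Withdrawals, full | Reaction shown | Reaction, full |
|---|---|---|---|---|
| 1 | 0/23 | 1/24 = 4.2% | 4/23 = 17.4% | 5/24 = 20.8% |
| 3 | 0/21 | 3/24 = 12.5% | 4/21 = 19.0% | 7/24 = 29.2% |
| 6 | 0/18 | 6/24 = 25.0% | 4/18 = 22.2% | 10/24 = 41.7% |

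k = 6 equals 24 − 18, the gap between the planned and evaluable numbers in Protocol 10.2. It is an outer value, not a forecast: non-evaluable may also mean oral lead-in dropout or missing data.

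The chance of at least one leaver among 24 is 1 − (1 − r)^24. At assumed leaving rates r of 2%, 5% and 10% this is 38%, 71% and 92%.

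**The case against.** Several points on the other side are sound and limit the finding.

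- **Most treatment stoppers are kept.** A reader might infer that the interim hides everyone who stopped early, for example anyone taken off injections for a related Grade 3 reaction. The documents do not support that. Protocol 7.1 moves such a participant into follow-up, and the Follow-up Week 4 limb of the rule then admits them. Only a person who also leaves the study before Week 4 is affected.
- **Waiting for Week 4 is not in itself a bias.** A participant who has stopped injections but is still followed enters at Follow-up Week 4, and a continuing participant enters at Injection 2. Both fall at about Week 4 ± 3 days, so this delay does not depend on outcome.
- **The wording can be read kindly.** Not having completed a visit yet suggests someone still in progress, and SAP 10.7.1 keeps withdrawn participants by default. That is a fair reading of intent. It does not settle the matter, because the default yields to any specific rule and the interim exclusion is one.
- **The reach is narrow.** SAP 10.10.3 attaches the exclusion to this one deliverable, not to the injection-phase-complete or end-of-study deliverables. The Study Team review after all of Cohort 4b completes Week 8 is separate (SAP 3.1, item 7). Table 2.5 might seem to belong on the list, but its title limits it to Cohort 4h.
- **The sizes are constructed.** The documents give no number of early leavers, and the reaction rates above assume that every leaver had the reaction.

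**Conclusion.** The point holds in a limited form. As written, the rule can remove a Cohort 4b participant who had Injection 1 and left before completing either qualifying visit. That person's data would then be missing from the interim displays named above, including the listings whose purpose is to show such cases.

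A reader might go further and conclude that the disseminated Cohort 4b tolerability results will be biased favourably. The documents do not support that as a certainty. It requires the literal reading, at least one leaver in the roughly four-week window, and a departure linked to poor tolerability. If nobody leaves in that window, there is no effect. If someone does, the interim shows no such withdrawals, where the full figure would be 4.2% for one leaver or 12.5% for three, assuming all 24 were injected.

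This is still worth correcting before the cut-off, because it is a stated rule that can give a wrong result in an analysis meant for dissemination.

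**What to change.** In SAP 3.2, 4 and 10.10.3, replace the visit-completion test with time since Injection 1. Include every Cohort 4b participant whose Injection 1 was early enough for the Week 4 window (Day 28 + 3 days = Day 31) to have passed by the cut-off, whether or not they stayed in the study. Exclude only those dosed more recently.

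In addition, list SAEs, withdrawals and AEs leading to discontinuation for all injected Cohort 4b participants, and state how many are excluded from the summary tables.

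A rule based on status, which admits anyone who has discontinued and holds back those still on treatment between injections, looks simpler but biases rates the other way. Suppose 12 participants qualify with no discontinuation and 6 more were injected recently, of whom 1 stops. The status rule shows 1/(12 + 1) = 7.7%, against 1/(12 + 6) = 5.6% of those dosed. The time rule treats participants injected on the same day alike.

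The cost is one sentence in three places and a small amount of programming, with no new data. A participant given Injection 2 early in its window would enter the tables a few days later than now. Results stay pooled across the topical treatments, so blinding in Cohort 4b is kept.

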3.3. Final Analyses

The final planned primary analyses will be performed after the completion of the following sequential steps:

1. All participants have completed the study (52-week follow-up phase) as defined in the protocol.
2. All required database cleaning activities have been completed and final DBR, source database lock (SDL), and DBF have been declared by Data Management.

4. ANALYSIS POPULATIONS

For the Cohort 1-5 preliminary interim analysis, displays will exclude Cohort 4b data from participants who have received injection 1 but have not yet completed Injection 2 Day 1 or Follow-up Week 4 by the data analysis cut-off. Cohort 4b will remain blinded to the randomized mitigation treatments **CCI** and results will not be presented by mitigation group for the interim analysis.

Population	Definition / Criteria	Analyses Evaluated
Screened	All participants who were screened for eligibility.	
 Study Population
Enrolled	
All participants who passed screening and entered the study.
 
Note: screening failures (who never passed screening even if rescreened) and participants screened but never enrolled into the study are excluded from the Enrolled population as they did not enter the study.
	
 Study Population
Randomized	All participants who were randomly assigned to treatment in the study.	
 Study Population
Safety	
All participants who received at least one dose of study treatment (oral or injection).
 
This population will be based on the treatment the participant received.
	
 Safety, Baseline and Demographic Characteristics
Safety – LA Exposed	
All participants who received at least one injection of long-acting study treatment.
 
This population will be based on the treatment the participant received.
	
 Injection Site Reactions
Pharmacokinetic	
All participants in the Safety population who received study treatment and had at least 1 non-missing PK assessment (non-quantifiable [NQ] values will be considered as non-missing values).
 
Note: PK samples that may be affected by protocol deviations will be reviewed by the study team to determine whether or not the sample will be excluded.
	
 PK Concentration and PK Parameter

Refer to [Appendix 10: List of Data Displays](#) which details the population used for each display.

4.1. Protocol Deviations

Important protocol deviations (including deviations related to study inclusion/exclusion criteria, conduct of the trial, participant management, or participant assessment) will be summarized and listed.

Protocol deviations will be tracked by the study team throughout the conduct of the study.

- Data will be reviewed prior to unblinding and DBF to ensure all significant deviations and deviations which may lead to exclusion from the analysis populations are captured and categorised on the protocol deviations dataset.
- This dataset will be the basis for the summaries and listings of protocol deviations.

A separate listing of all inclusion/exclusion criteria deviations will also be provided. This listing will be based on data as recorded on the inclusion/exclusion page of the electronic case report form (eCRF).

5. CONSIDERATIONS FOR DATA ANALYSES AND DATA HANDLING CONVENTIONS

5.1. Study Treatment & Sub-group Display Descriptors

In general, the following treatment group descriptors will be presented in data displays for reporting, with minor variations depending on whether a display is presenting treatment group information as a column or row.

For Cohort 4b, all data will be summarized by period (OLI, injection 1, injection 2, follow-up, overall) and selected safety and patient reported outcome endpoints will also be summarized by CCI PK concentrations and parameters will also be summarized by treatment sequence and period, as appropriate.

Treatment Group Descriptions					
		Randomization		Data Displays for Reporting	
Part	Arm	Code	Description	Description	Order in TLF
Part 1	C1 CAB 400	A1	CAB 400 mg/mL IM injections 4-weeks apart in gluteus muscle (cohort 1)	Oral CAB 30 mg QD	1
				Inj.1 600 mg IM Gluteal	2
				Inj.2 400 mg IM Gluteal	3
				Follow-up	4
				Overall ¹	5
	C1 CAB 200	C1	CAB 200 mg/mL IM Injection 4-weeks apart in gluteus muscle (cohort 1)	Oral CAB 30 mg QD	6
				Inj.1 600 mg IM Gluteal	7
				Inj.2 400 mg IM Gluteal	8
				Follow-up	9
				Overall ¹	10
	C2 CAB 400	A2	CAB 400 mg/mL SC injections 4-weeks apart in abdomen (cohort 2)	Oral CAB 30 mg QD	11
				Inj.1 600 mg SC Abdomen	12
				Inj.2 200 mg SC Abdomen	13
				Follow-up	14
				Overall ¹	15
	C2 CAB 200	C2	CAB 200 mg/mL SC injections 4-weeks apart in abdomen (cohort 2)	Oral CAB 30 mg QD	16
				Inj.1 300 mg SC Abdomen	17
				Inj.2 100 mg SC Abdomen	18
				Follow-up	19
				Overall ¹	20
	C3 CAB 400	A3	CAB 400 mg/mL IM injections 4-weeks apart in	Oral CAB 30 mg QD	21
				Inj. 1 600 mg IM Lateral Thigh	22
				Inj. 1 400 mg IM Lateral Thigh	23

			lateral thigh (cohort 3)	Inj. 2 400 mg IM Lateral Thigh	24
				Follow-up	25
				Overall ¹	26
	C3 CAB 200	C3	CAB 200 mg/mL IM injections 4- weeks apart in lateral thigh (cohort 3)	Oral CAB 30 mg QD	27
				Inj.1 600 mg IM Lateral Thigh	28
				Inj.1 400 mg IM Lateral Thigh	29
				Inj.2 400 mg IM Lateral Thigh	30
				Follow-up	31
				Overall ¹	32
	C4 CAB 400	A4	CAB 400 mg/mL Injections 4-weeks apart (first IM injection in gluteus medius and second SC injection in abdomen; cohort 4)	Oral CAB 30 mg QD	33
				Inj.1 400 mg IM Gluteal	34
				Inj.2 200 mg SC Abdomen	35
				Follow-up	36
				Overall ¹	37
	C4 CAB 200	C4	CAB 200 mg/mL Injections 4-weeks apart (first IM injection in gluteus medius and second SC injection in abdomen; cohort 4)	Oral CAB 30 mg	38
				Inj.1 400 mg IM Gluteal	39
				Inj.2 100 mg SC Abdomen	40
				Follow-up	41
				Overall ¹	42
	C4b CAB 400 + Topical Steroid or NSAID 4	A4bG1	CAB 400 mg/mL Injections 4- weeks apart in CCI	Oral CAB 30 mg QD	43
				CCI	44
				CCI	45
				Follow-up	46
				Overall ¹	47
	C4b CAB 400 + Topical Steroid or NSAID 4	A4bG2	CAB 400 mg/mL Injections 4- weeks apart in CCI	Oral CAB 30 mg QD	4833
				CCI	49
				CCI	50
				Follow-up	51
				Overall ¹	52
		A4h		Oral CAB 30 mg QD	53

	C4h CAB 400 + rHUPH20		CAB 400 mg/mL Injection in the abdomen with rHuPH20	Inj. 1 CAB 400 mg + 5000 U rHUPH20 SC Abdomen	54
				Follow-up	55
				Overall ¹	56
	C4h CAB 200 + rHUPH20	A4h	CAB 200 mg/mL Injection in the abdomen with rHuPH20	Oral CAB 30 mg QD	57
				Inj. 1 CAB 400 mg + 5000 U rHUPH20 SC Abdomen	58
				Follow-up	59
				Overall ¹	60
	N/A	N/A	Pooled Group ²	Pooled Oral CAB 30 mg QD OLI ONLY	61
				Pooled Oral CAB 30 mg QD	62
				Pooled CAB 400 mg/mL Q4W 400 mg IM Gluteal	63
				Pooled CAB 200 mg/mL Q4W 400 mg IM Gluteal	64
				Pooled CAB 400 mg/mL Q4W 200 mg SC	65
				Pooled CAB 200 mg/mL Q4W 100 mg SC	66
				Pooled CAB 400 mg/mL Q4W 400 mg Lateral Thigh	67
				Pooled CAB 200 mg/mL Q4W 400 mg Lateral Thigh	68
Part 2	C5 CAB 400 ³	A5	CAB 400 mg/mL IM injections 12-weeks apart in gluteus muscle (cohort 5)	Oral CAB 30 mg QD	69
				Inj. 1 800 mg IM Gluteal	70
				Follow-up	71
				Overall ¹	72
	C5 CAB 200	C5	CAB 200 mg/mL IM injections 12-weeks apart in gluteus muscle (cohort 5)	Oral CAB 30 mg QD	73
				Inj. 1 400 mg IM Gluteal	74
				Follow-up	75
				Overall ¹	76
	N/A	N/A	Historical Data, CAB 200 mg/mL	(ATLAS/FLAIR) Inj. 1 CAB 600 mg IM Gluteal ³	77
				(ATLAS/FLAIR) Inj. 2 CAB 400 mg IM Gluteal ³	78
				(ÉCLAIR) Inj. 1 CAB 800 mg IM Gluteal ³	79

Note: A1 = Active Drug in Cohort 1; A2 = Active Drug in Cohort 2; A3 = Active Drug in Cohort 3; A4 = Active Drug in Cohort 4; A4h = Active Drug in Cohort 4h; A5 = Active Drug in Cohort 5; A6 = Active Drug in Cohort 6; C1 = Cohort 1, C2 = Cohort 2, C3 = Cohort 3, C4 = Cohort 4, C4b = Cohort 4b, C4h = Cohort 4h, C5 = Cohort 5.

1. Overall group is not applicable for PK analyses.
2. Pooled active and AC groups are only applicable when there is more than one cohort at the stated dose (mg) to combine for the specific summary.
3. Historical data for formulation of 200 mg/mL from the Phase 3 program, only applicable for PK analyses.

Treatment comparisons for the PK pairwise and cross study historical comparison (See Section 8.1.5) will be displayed by injection using the following descriptors:

Pairwise Comparisons for AUC(0- τ), C_{max}, and C _{τ} :

Injection 1 (CAB 400 mg/mL):

1. C2 CAB400 - Inj. 1 600 mg SC Abdomen vs C1 CAB400 - Inj. 1 600 mg IM Gluteal
2. C3 CAB400 - Inj. 1 600 mg IM Lateral Thigh vs C1 CAB400 - Inj. 1 600 mg IM Gluteal
3. C2 CAB400 - Inj. 1 600 mg SC Abdomen vs C3 CAB400 - Inj. 1 600 mg IM Lateral Thigh
4. C4h CAB400 + rHUPH20 - Inj. 1 CAB 400 mg + 5000 U rHUPH20 SC Abdomen vs C4 CAB400 - Inj. 1 400 mg IM Gluteal

Injection 2 (CAB 400 mg/mL):

1. C3 CAB400 - Inj. 2 400 mg IM Lateral Thigh [participants who received 600 mg for Injection 1] vs C1 CAB400 - Inj. 2 400 mg IM Gluteal

Historical Comparisons:

Injection 1 (CAB 400 mg/mL):

1. C1 CAB400 - Inj. 1 600 mg IM Gluteal vs Week 4 post injection 1 in ATLAS/FLAIR IM Gluteal CAB 600 mg (CAB 200 mg/mL) Q4W
2. C2 CAB400 - Inj. 1 600 mg SC Abdomen vs Week 4 post injection 1 in ATLAS/FLAIR IM Gluteal CAB 600 mg (CAB 200 mg/mL) Q4W
3. C3 CAB400 - Inj. 1 600 mg IM Lateral Thigh vs Week 4 post injection 1 in ATLAS/FLAIR IM Gluteal CAB 600 mg (CAB 200 mg/mL) Q4W
4. C4 CAB400 - Inj. 1 400 mg IM Gluteal vs Week 4 post injection 1 in ATLAS/FLAIR IM Gluteal CAB 600 mg (CAB 200 mg/mL) Q4W [dose normalize to 400 mg]
